8.1.1 Determination of Sample Size

A total of 60 patients (30 per arm) is based on the assumption that the rate of MRD negative disease that is approximately 20% higher in the experimental arm vs. the control arm will be considered promising for further evaluation. Because this is a proof of concept phase II randomized trial rather than a confirmatory trial, the comparison will be made using a one-sided test at 80 % power and at most 10% type I error. Table 8.1 below shows the detectable difference depending on the control rate. Boldfaced figures are values assumed most likely based on the literature and previous studies. Calculations are based on a Cochran-Mantel-Haenszel test with continuity correction.

Table 8-1 Detectable increases in the rate of MRD with 80 %power (one-sided $\alpha=0.10$)

Control Arm	Experimental Arm	Difference
2.5%	21.8 %	19.3 %
5.0%	26.7 %	21.7 %
10.0%	35.5 %	25.5%
15.0%	42.4%	27.4%
20.0%	48.1 %	28.1 %

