8. STATISTICAL AND QUANTITATIVE ANALYSES

8.1 Statistical Methods

A total of 60 patients will be enrolled in a 1:1 ratio stratified according to level of response (<VGPR vs \geq VGPR) and presence or absence of at least one poor prognostic risk factor (Yes to at least one cytogenetic risk factor including del-13 or hypodiploidy by karyotyping, or any of t(4;14), t(14;16), t(14;2), del17p, 1q21 gain by FISH. The primary objective of this study is to compare the rate of MRD at 12 months between the two arms. Because this is a proof of concept trial rather than a confirmatory trial, the comparison will be made using one-sided test at 80% power and at most 10% type I error. The outcome will be considered promising and warrant evaluation with phase III trial if MRD negative disease is 20% higher in the experimental arm vs. the control arm. This assumption is based on the following data:

- 1) While it is well established that CR rate may increase over time post-transplant, even without any maintenance (in the IFM study, at randomization to lenalidomide maintenance or placebo 5% and 8% of patients were in CR, but ultimately 29% and 27%, respectively achieved CR; Attal et al, N Eng J Med, 2012), the conversion to CR on lenalidomide maintenance in patients with established persistent measurable disease is expected to be less than 5%
- 2) CR rate to lenalidomide alone is estimated < 5% in newly diagnosed myeloma (Rajkumar et al, Blood 2005).
- 3) While there is not published data on the rate of conversion from less than MRD-negative to MRD-negative disease while on lenalidomide maintenance, it is estimated that only a small proportion of patients on lenalidomide arm (which we estimate to be < 5% and/or not to be clinically significant) will convert to MRD-negative status because of delayed effect of transplant and/or lenalidomide treatment.
- 4) Based on experience from the CRd trial ([name] et al, ASCO 2013), approximately 20% of patients have a potential to convert from less than MRD-negative to MRD-negative disease between 8 and 20 months (1-year) of the CRd treatment.

Together, these observations provided rationale for 12 months of duration of treatment and statistical design: an increase of the rate of MRD-negative disease by 20% - 28% in the experimental arm versus control arm was used for calculation of sample size (as for example 26.7 % rate in the experimental arm and 5% in control arm).

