8.1.6 Efficacy Analysis

The primary objective of this study is to compare the rate of MRD at 12 months between the two arms. Because this is a proof of concept trial rather than a confirmatory trial, the comparison will be made using a one sided test at the 10% significance level. This comparison will be performed using (i) a chi-square or Fisher's exact test comparing the two treatment arms, and (ii) a Cochran Mantel-Haenszel (CMH) test stratified by VGPR status and risk factors vs. no risk factors. We anticipate 20-30% of pts will be high risk and 20-40% will be in less than a VGPR at study entry. Therefore, in the event of small stratum sizes (<5 per stratum in either treatment arm), we will conduct an exact logistic regression analysis in place of the CMH test (Hirji, Mehta, and Patel, et al., 1987).

Secondary objectives include the overall response rate, defined as at least a partial response to therapy (>PR), at least VGPR (>VGPR) and at least nCR rate (>nCR), CR, and sCR rates, time to progression, duration of response, and progression-free and overall survival. The rate of overall response will be reported along with its exact 95% binomial confidence interval. Time to event endpoints will be estimated using the product-limit method of Kaplan and Meier. Follow-

up time for these endpoints will be calculated from the date of randomization. For time to progression, patients that do not experience progression during follow-up will be censored on the date of their last clinical examination. Duration of response will be assessed conditional upon achieving at least a partial response. Follow-up time for this endpoint will be calculated from the date of the clinical examination, which confirmed the response, until the date of disease progression, or censoring at the date of last clinical follow-up. For progression-free survival, follow-up time will continue from the date of randomization until the date of documented disease progression or death. Patients who do not reach either milestone during follow-up will be censored on their date of last clinical assessment.

Correlative biomarkers will be assessed for association with response in the experimental arm using nonparametric tests given the relatively small number of responders anticipated (20%). A Wilcoxon rank-sum test will be used to compare baseline (pre-treatment) biomarker levels in the responders vs. non-responders.

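### Table 8-1 is right, but an exact 20-point gain (75%) and a 20% experimental rate (58%) fall short of 80% power at 5% control, and the uncorrected chi-square that 8.1.6 allows exceeds the 10% error limit

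*Combined protocol and SAP*

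**What the plan says.** **Effect size.** Section 8.1 calls the result promising "if MRD negative disease is 20% higher in the experimental arm vs. the control arm". Section 8.1.1 softens this to a "rate of MRD negative disease that is approximately 20% higher in the experimental arm vs. the control arm", and Section 1.9 hypothesizes a 20% increase. Section 8.1 then says that increases of 20% to 28% were used for the sample size, with 26.7% vs 5% as the example.

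**Evidence.** Section 8.1 estimates conversion to MRD negativity on lenalidomide alone at below 5%. For the triplet it cites a carfilzomib-lenalidomide-dexamethasone (CRd) trial in which "approximately 20% of patients have a potential to convert from less than MRD-negative to MRD-negative disease".

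**Design.** "A total of 60 patients (30 per arm) is based on the assumption" of that difference, and "the comparison will be made using a one-sided test at 80 % power and at most 10% type I error". Table 8-1 lists the experimental rates detectable with 80% power: 21.8%, 26.7%, 35.5%, 42.4% and 48.1% against control rates of 2.5%, 5%, 10%, 15% and 20%. "Calculations are based on a Cochran-Mantel-Haenszel test with continuity correction".

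**Analysis.** Section 8.1.6 plans "a chi-square or Fisher's exact test comparing the two treatment arms", alongside a stratified Cochran-Mantel-Haenszel (CMH) test that is replaced by exact logistic regression if strata are small. It gives no rule for choosing between the two unstratified tests and does not say whether the chi-square is continuity-corrected.

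**The concern.** The same figure, 20%, serves as a criterion for success, as an approximate design difference and as a conversion rate in a cited trial. Only the Table 8-1 pairs carry the 80%. At 5% control the table requires 21.7 points, which is more than the flat criterion of 20. A 20% experimental rate over 5% control would be a gain of only 15 points. A reader who attaches 80% to these 20% statements would credit the trial with more sensitivity than it has and could read too much into a negative result.

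The choice of test matters for a related reason. With few conversions expected in the control arm, the candidate tests differ widely in true error rate and in power. Leaving the choice open leaves both undetermined, and one permitted choice breaks the plan's own error limit.

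**Working it through.** **Inputs.** n = 30 per arm and one-sided alpha 0.10 (8.1.1); control rate below 5% and CRd conversion about 20% (8.1); permitted tests (8.1.6).

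**Method.** Let X_C ~ Bin(30, p_C) and X_E ~ Bin(30, p_E). For a given test,

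power = Σ P(X_C = i) · P(X_E = j), summed over all (i, j) in the 31 × 31 table that the test rejects.

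Setting p_C = p_E gives the true type I error.

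**Step 1: reproduce Table 8-1.** Solving for 80% power with Fisher's test gives experimental rates of 21.8%, 26.7%, 35.5%, 42.4% and 48.1%. All five rows match. The continuity-corrected chi-square gives the same powers. Other methods do not fit the rows: the normal approximation without correction gives 85% to 87%, and the uncorrected chi-square by enumeration gives 87% to 90%.

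**Step 2: power for the 20% statements (Fisher or corrected chi-square).**

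| Control | Experimental | Gain (points) | Power |
|---|---|---|---|
| 5% | 26.7% (Table 8-1) | 21.7 | 80.0% |
| 5% | 25% | 20 | 75.3% |
| 2.5% | 22.5% | 20 | 81.9% |
| 10% | 30% | 20 | 65.0% |
| 5% | 20% | 15 | 57.6% |
| 2.5% | 20% | 17.5 | 73.9% |
| 1% | 20% | 19 | 83.0% |
| 0% | 20% | 20 | 87.7% |

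An exact 20-point gain reaches 80% only if control is about 3.2% or lower. A 20% experimental rate reaches 80% only if control is about 1.5% or lower.

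**Step 3: true type I error against the 10% limit.**

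| Test | At a common 5% rate | Maximum over all rates |
|---|---|---|
| Uncorrected chi-square | 11.7% | 12.3% |
| Fisher's exact | 1.9% | 7.8% |

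Power at 25% vs 5% is 85.4% with the first and 75.3% with the second.

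An example shows the gap. Suppose no control patient converts.
- Uncorrected chi-square, 2 of 30 vs 0 of 30: the pooled rate is 2/60 = 0.0333, SE = √(0.0333 × 0.9667 × 2/30) = 0.0464, and z = 0.0667/0.0464 = 1.44. This exceeds 1.282, so two conversions are significant.
- Fisher, 3 vs 0: p = C(30,3)/C(60,3) = 4060/34220 = 0.119, not significant.
- Fisher, 4 vs 0: p = 27405/487635 = 0.056, significant.

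Two or three conversions against none would therefore be positive or negative depending on a choice the plan leaves open.

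**Step 4: a size-controlled alternative.** Boschloo's test orders the tables by the one-sided Fisher p-value. It raises the critical value as far as the maximum size over the common rate allows within 10%. With 30 per arm the maximum size is 9.7%. Power is 80.4% at 25% vs 5%, 84.4% at 26.7% vs 5%, 80.0% at 20% vs 2.5% and 64.3% at 20% vs 5%.

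**The case against.** The plan nowhere claims 80% power for exactly 20 points over 5%, or for 20% vs 5%. It says approximately 20%, sends the reader to Table 8-1 and gives 26.7% vs 5% as its example. The table is correct, and 19.3 or 21.7 points is fairly described as about 20. This stands: a reader might infer that the stated 80% is a miscalculation, and the documents do not support that.

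A reader might also infer that an absolute rate of 20% was mistaken for a difference. That is not established. The cited trial used another regimen, and the denominator of its 20% is not given. Section 1.9 describes the CRd result as an improvement of about 20% in the MRD-negativity rate. If that change was counted over all patients, conversion among those still positive would be higher. Assuming, for illustration, that 75% were still positive, it would be 0.20/0.75 = 26.7%.

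The 58% takes control at 5%, the top of the plan's range. The 20% responder rate in Section 8.1.6 belongs to the biomarker analysis and is not explicitly MRD negativity, so nothing here rests on it. The boldface marking the likeliest rows of Table 8-1 is not visible in the text reviewed, so the plan's expected row cannot be identified.

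On the test, Fisher's already respects the 10% limit, and 8.1.1 refers to a continuity correction. But 8.1.6 does not carry that correction over to the chi-square, so the uncorrected version remains permitted.

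**Conclusion.** The 80% is correct for the Table 8-1 pairs and should not be called an error. Two things remain.

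First, the 20% wording is looser than the design. At 5% control, the flat criterion has 75% power rather than 80%. An experimental rate of 20% has 58% there, the low end of a range that reaches 88% as control falls to 0%. These figures assume 30 evaluable patients per arm and Fisher's or the corrected test. To quote 58% alone as the power of the trial would be to quote the worst corner.

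Second, and independent of any view on the effect size, Section 8.1.6 permits a test with a true type I error of 11.7% at a 5% rate and up to 12.3% overall, against a stated limit of 10%. The other permitted test spends only 1.9% at that rate and gives up power.

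**What to change.** 1. In Sections 8.1 and 8.1.1, say that 80% power applies to the Table 8-1 pairs. Add the power for an exact 20-point gain (75% at 5% control, 82% at 2.5%) and for a 20% experimental rate over 0% to 5% control (88% to 58%). If change 2 is adopted, compute the printed figures with the test named there.
2. In Section 8.1.6, replace the choice of chi-square or Fisher's exact test with Boschloo's unconditional exact test at one-sided 10%. Keep the stratified CMH or exact logistic analysis as planned. Make the change before the 12-month results are compared by arm.

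The second change keeps the error limit and brings an exact 20-point gain over 5% to 80.4%. With Fisher's test the same power would take about 34 per arm. It does not rescue 20% vs 5%, which stays at 64.3%.

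The cost is wording in three sections and a less favourable stated power for the 20% scenarios. No patients are added.

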8.1.2 Randomization and Stratification

Patients will be randomized 1:1 and stratified based on criteria outlined in section 6.9 (VGPR status and risk factors vs. no risk factors). Randomization will occur between Day +70 and +120 post-transplantation. Initiation of maintenance therapy with study drug will begin between day +80 and +130. Prior to randomization, subjects must undergo disease re-staging, must have adequate organ function (ANC $\geq 1000\mu\text{L}$, platelet count $\geq 75,000\mu\text{L}$, creatinine clearance $\geq 30\text{mL/min}$, bilirubin $\leq 2\text{mg/dL}$, AST $\leq 3 \times \text{ULN}$, and Alk. Phos. $\leq 3 \times \text{ULN}$), and must have no evidence of progressive disease.

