4.3 Number of Patients

A total of 60 patients will be enrolled in a 1:1 ratio into one of two arms: IRd or lenalidomide alone. Enrollment is defined as the time of randomization. **Protocol treatment must start within 2 days of randomization.**

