5. STUDY POPULATION

5.1 Inclusion Criteria

Each patient must meet all of the following inclusion criteria to be enrolled in the study:

1. Patients who completed induction treatment followed by autologous stem cell transplant as initial therapy for symptomatic myeloma as per IMWG criteria and are considered for single agent lenalidomide maintenance or initiated single agent lenalidomide maintenance.
 - a) Patients will be eligible for enrollment in the first 0-6 months of lenalidomide maintenance provided that lenalidomide maintenance has been initiated within 6 months post transplant as per standard of care.
 - i. Patients do not have to be on Lenalidomide at the time of study consent.
 - b) Patients already in lenalidomide maintenance must be received lenalidomide 10 mg or 15 mg and be able to tolerate dose escalation to 25 mg daily.
 - c) Patients receiving off protocol lenalidomide maintenance cannot exceed 6 months post-transplant
 - d) A one week break from off protocol lenalidomide is suggested, prior to initiating treatment on the study
 - i. Any delays >7 days to align treatment with the start of Cycle 1 Day 1, of either arm, must be discussed with the PI.

- e) Patients who completed tandem transplantation will be eligible for enrollment
2. No evidence of progressive disease on lenalidomide
3. Evidence of minimal residual disease at the time of screening defined as at least MRD-positive disease.
 - a) The primary method of evaluation of MRD is Multi-parameter Flow Cytometry (MFC) performed at the University of Chicago.
 - b) Patients who have negative MRD by Multi-Parameter Flow Cytometry (MFC) but have residual original monoclonal protein by serum or urine immunofixation may be eligible if they are found to have MRD-positive disease by Next Generation Sequencing (NGS)
 - c) If patient is receiving lenalidomide, any delays required to align treatment with the start of Cycle 1 of either arm, must be discussed with the PI.
4. Bone marrow specimen from diagnosis (or pre-induction) will be required at study entry; available DNA sample will be used for calibration step for MRD evaluation by gene sequencing
5. Males and females ≥ 18 years of age
6. Life expectancy of more than 3 months
7. ECOG performance status of 0-2
8. Adequate hepatic function, with bilirubin $\leq 1.5 \times$ ULN and aspartate aminotransferase (AST) and alanine aminotransferase (ALT) $\leq 3 \times$ ULN

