6. REGISTRATION PROCESS

When a potential patient has been identified, notify the CRA via phone or email to ensure a reservation on the study (contact information listed on enrollment form). Reservations for potential subjects will only be held for subjects who have signed consent for that particular study.

When registering a subject, the following must occur:

- Confirm that the institution has a current IRB approval letter for the correct version of protocol/consent and has an annual update on file, if appropriate.
- Submit all required materials (Eligibility Checklist, Source documentation, & signed consent form) to confirm eligibility and required pre-study procedures to the CRA a minimum of 48 hours prior to the subject's scheduled therapy start date.
- Source documentation includes copies of all original documents that support each inclusion/exclusion criteria. The eligibility checklist does not serve as source documentation but rather as a checklist that original source documentation exists for each criterion.
- Communicate with the CRA to ensure all necessary supporting source documents are received and the potential subject is eligible to start treatment on schedule. If there are questions about eligibility, the CRA will discuss it with the PI. PI may clarify, but not overturn, eligibility criteria.
- Affiliate sites must confirm registration of subjects by obtaining a subject study ID number from the CRA via phone, fax or email.
- If a subject does not start on the scheduled day 1 treatment date, promptly inform the CRA as the delay in start may deem the subject ineligible and/or require further or repeat testing to ensure eligibility.
- The date the patient is randomized if randomization is involved or receives treatment for the first time will be considered the patient's "On Study Date." The patient's subject ID will be assigned and a confirmation of registration will be issued by the CRA on this date. Subjects that sign consent and do not go "On Study" will be recorded in the database with the date they signed consent and the reason for not going "On Study" (e.g., Ineligible, Screen Failure or Withdrawn Consent).

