patient is rendered non-evaluable, a new patient will be randomized into the trial to preserve the sample size for primary endpoint analysis. Patients enrolled in this trial will be patients who completed initial induction followed by autologous stem cell transplant for symptomatic myeloma (per IMWG criteria) and in the first 0-6 months of Lenalidomide maintenance provided that was initiated within 6 months after transplant as per standard of care and with at least MRD-positive residual myeloma. The study's primary endpoint, attainment of MRD-negative disease by MFC will be assessed at the completion of the 12 cycle of protocol treatment (both arms). In patients that were enrolled based on their MRD-positivity by MFC, an improvement will be counted when these patients switch to MRD-negative disease by MFC at the 12-month time-point. Patients that were enrolled per their MRD-positivity by NGS will require NGS analysis to determine their MRD status at 12 months of treatment. In this patient population, only a switch from MRD-positivity to negativity by NGS will be counted as an improvement. We anticipate that no more than 10% of patients will be enrolled who are MFC negative but NGS positive. If there is an imbalance between the two treatment arms in this variable we will adjust by post-hoc stratification or covariate analysis. All patients enrolled and receiving any IRD or R treatment will be evaluable for this endpoint, with the exception of patients that decline to receive treatment for reasons unrelated to toxicity and/or efficacy. Patients in that category will be replaced. All other patients who discontinue treatment before receiving 12 cycles of protocol treatment will be considered treatment failures for assessment of the study's primary endpoint. The proportion of MRD-negative patients will be reported along with 95% confidence intervals.

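### The entry and timing rules in 8.1.2, 5.1, 4.3 and 7.9 disagree, and the protocol does not say which governs

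*Combined protocol and SAP*

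**What the plan says.** **Randomisation window.** Section 8.1.2: "Randomization will occur between Day +70 and +120 post-transplantation". Section 5.1, item 1a: "Patients will be eligible for enrollment in the first 0-6 months of lenalidomide maintenance", with lenalidomide begun within 6 months of transplant. Item 1c: "Patients receiving off protocol lenalidomide maintenance cannot exceed 6 months post-transplant". The populations text in section 8 repeats the rule in 5.1: "in the first 0-6 months of Lenalidomide maintenance provided that was initiated within 6 months after transplant". Section 4.3 ties the two together: "Enrollment is defined as the time of randomization".

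**Treatment start.** Section 8.1.2: "Initiation of maintenance therapy with study drug will begin between day +80 and +130". Section 4.3: "Protocol treatment must start within 2 days of randomization".

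**Organ function.** Sections 5.1 and 8.1.2 each give a mandatory list of laboratory limits, and the lists differ.

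**Stratifying response.** The summary and 4.1 place the assessment at screening. Section 7.9 names screening twice and, between the two mentions, inserts a point three months after lenalidomide maintenance starts.

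**Who decides.** Section 6 provides for central eligibility review and adds: "PI may clarify, but not overturn, eligibility criteria".

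**The concern.** Because enrolment and randomisation are the same event, 5.1 and 8.1.2 set two different windows for it. The start rules in 8.1.2 and 4.3 cannot both be followed on part of the window in 8.1.2. The two organ-function lists would accept different patients. Response level is a stratification factor, so the time at which it is read should be unambiguous.

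At stake is whether a given patient is eligible, and whether a given start date is compliant. The renal item also bears on patient safety: as printed, inclusion 10 screens nobody out on renal function.

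**Working it through.** There is no plan figure to reproduce. The check sets the rules side by side and counts days.

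**1. Randomisation window** (30.44 days per month)
- 8.1.2: Days +70 to +120, which is 120 − 70 + 1 = 51 days.
- 5.1 with item 1c applied: 6 × 30.44 = 182.6, about Day +183, or 183 − 120 = 63 days beyond 8.1.2.
- 5.1 with item 1a read alone: (6 + 6) × 30.44 = 365.3, about Day +365, or 365 − 120 = 245 days beyond. This reading ignores item 1c.
- Days before +70 are open under 5.1 and closed under 8.1.2.

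**2. Start rule.** A patient randomised on day d must start by d + 2 (4.3) and no earlier than Day +80 (8.1.2). Both hold only if d + 2 ≥ 80, so d ≥ 78.
- Days +70 to +77 fail: 8 of 51.
- Days +78 to +120 pass: 43 of 51.
- At the other end, 120 + 2 = 122, so start days +123 to +130 in 8.1.2 cannot be reached under 4.3.
- If the randomisation day counts as the first of the 2 days, the clash covers 9 days (+70 to +78).

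**3. Organ function**

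| Item | 5.1 | 8.1.2 |
|---|---|---|
| Renal | CrCl ≥50 mL/min, or serum creatinine under 2 (printed g/dL) | CrCl ≥30 mL/min |
| Bilirubin | ≤1.5 × ULN | ≤2 mg/dL |
| Alkaline phosphatase | none | ≤3 × ULN |
| ALT | ≤3 × ULN | none |
| Haemoglobin | ≥8 g/dL | none |
| ANC, platelets, AST | same limits | same limits |

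In g/dL the creatinine limb is met by every patient. Appendix 14.2 works in mg/dL, so the unit is probably a slip. Assuming mg/dL, with illustrative patients of my own choosing and the Cockcroft-Gault equation:
- Woman, 60 kg, creatinine 1.9 mg/dL: CrCl = 0.85 × (140 − age) × 60 / (72 × 1.9). This gives 30.2 at age 59, 29.8 at 60 and 26.1 at 70. She passes inclusion 10 on creatinine and fails 8.1.2 from age 60.
- Man, 80 kg, creatinine 2.1 mg/dL: CrCl = (140 − age) × 80 / (72 × 2.1). This gives 49.7 at age 46, 39.7 at 65 and 30.2 at 83. He fails inclusion 10 and passes 8.1.2 at ages 46 to 83.

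Neither renal rule contains the other. The bilirubin limits cross at ULN = 2 / 1.5 = 1.33 mg/dL. Below that the limit in 5.1 is stricter; above it the limit in 8.1.2 is. The documents give no laboratory ULN.

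**4. Stratifying response.** Criterion 1 in 5.1 admits patients who are only being considered for lenalidomide, and those in its first three months. The three-month point in 7.9 cannot apply to them. Inside the window in 8.1.2, three months of post-transplant lenalidomide is impossible before Day +84 (three months as 84 days) or Day +91 (as 91 days):
- Days +70 to +83 are 14 of the 51 days; Days +70 to +90 are 21.
- Even at Day +120, lenalidomide must have begun by Day 120 − 84 = +36 or 120 − 91 = +29.

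Section 1.9 also says every enrolled patient is already on lenalidomide, which criterion 1 does not require.

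**5. Cross-references.** Section 8.1.2 cites section 6.9 for the strata, which are in 7.9. Inclusion 10 cites 13.2 for the equation, which is in 14.2.

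**The case against.** The strongest reply is that the rules are cumulative. Both lists are mandatory, so a patient could be required to meet both, with the stricter limit binding; limits found in only one list are then additions, and Days +70 to +120 fall inside the broader period in 5.1. Much of this is workable, but the protocol never says so. The reading also makes part of 5.1 empty: by Day +120 a patient can have had at most 120 / 30.44 = 3.9 months of post-transplant lenalidomide, so the later part of the 0–6 month allowance could never be used. It does not make Days +70 to +77 compliant, and it does not settle 7.9.

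Several narrower points stand:
- The 8 of 51 counts calendar days, not patients. A site can comply by randomising on Days +78 to +120.
- Item 1c sits in the same criterion as 1a, so Day +183 is the more natural upper end; Day +365 needs 1a read alone.
- The three-month phrase in 7.9 looks like leftover text, since screening is named on both sides of it. It is still in the current wording.
- Section 1.9 is background, not an entry rule.
- The renal patients are assumed. They show that the rules are not equivalent, not how many patients are affected.
- Central review makes divergence between centres less likely. It ranks no section, and the PI cannot overturn a criterion.
- The ITT population is defined by receiving a dose, so an entry deviation alone removes nobody from it.
- This version is dated 25 September 2019 and accrual ends by 31 March 2020, so corrected entry wording would govern only about six months of accrual.

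**Conclusion.** The concern holds and should be fixed. The start-rule clash on 8 of 51 randomisation days follows directly from the text, on the ordinary reading of the 2-day limit (9 days if the randomisation day is counted). The two windows differ by about 63 days at the upper end with item 1c applied, and 5.1 has no lower limit. The organ-function lists differ on renal function, bilirubin, alkaline phosphatase, ALT and haemoglobin. The finding that the renal rules are not nested assumes mg/dL was meant in inclusion 10; as printed, its creatinine limb excludes nobody. The 7.9 item is the weakest part, probably an editing remnant, but it touches a stratification factor.

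The consequence is uncertainty about eligibility and protocol compliance.

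**What to change.** The sponsor and clinical team should reconcile 8.1.2, 5.1, 4.3, 7.9, 1.9 and the protocol summary so that the protocol contains:
- one randomisation window, with items 1a and 1c made consistent with it;
- one treatment-start rule that can be met on every permitted randomisation day;
- one organ-function list, with the unit and the either/or construction in inclusion 10 checked;
- one time for reading the stratifying response.

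State each rule once and have the other sections refer to it. Neither renal rule should be deleted until inclusion 10 has been corrected, because as printed it provides no renal screen. Correct the references to 6.9 and 13.2 at the same time. Which limits and windows are right is for the clinical team; none is proposed here.

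The cost is protocol amendment wording only.
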